7.3.3 CompAQ for Facial and Truncal Acne

It will be collected at baseline, week 12 and 24/ early termination. The Investigator or designee should provide the subject (16 years of age and older) with the comprehensive QoL measure inclusive of facial and truncal form and instruct the subject to read and answer all 20 quality of life questions. The questionnaire will measure the impact of facial and torso acne on health-related quality of life.

The 20 questions consists of 5 domains that assess a variety of psychosocial and physical impacts of acne: Psychological/Emotional, Social (Judgement From Others), Social Interactions, Treatment Concerns, Physical Symptoms. The score on the CompAQ has a possible range of 0 to 160. The higher the score, the more quality of life is impaired. For instructions of use and scoring (Chelsea McLellan, Marc P. Frey, Diane Thiboutot, Alison Layton, Mary-Margaret Chren, Jerry Tan, Development of a Comprehensive Quality-of-Life Measure for Facial and Torso Acne. Journal of Cutaneous Medicine and Surgery First Published January 31, 2018 <https://doi.org/10.1177/1203475418756379>)

An anchor question is added in order to detect responsivity with intervention and for Minimal Clinically Important Difference (MCID).

Higher scores indicate greater adverse impact

- The response range for each question is from 0–8 with higher numbers indicating greater adverse impact.
- For each domain, response range is from 0–32.
- For the long form questionnaire, response range is from 0–160
- For the short form questionnaire, response range is from 0–40

The investigator or delegate will then check all questions of the questionnaire for completeness prior to the subject leaving the office.

7.3.4 EuroQoL 5-Dimension (EQ-5D-5L)

At baseline and weeks 12 and 24/Early termination, subject will complete the EQ-5D-5L (Appendix 13.6).

EQ-5D-5L is a validated questionnaire for the assessment of the general health state. It contains two parts: a descriptive system and a VAS. The descriptive system is made up of five dimensions: mobility, self-care, usual activities, pain/discomfort and anxiety/depression. The VAS consists of a vertical line where the subject can assess his or her own health status. EQ-5D-5L will be administered according to the schedule of assessments only to the subset of subjects who fluently speak a language in which the questionnaire is presented (based on availability of validated translations in participating countries).

7.3.5 Subject satisfaction questionnaire

At weeks 12 and 24/Early termination, subject will complete a satisfaction questionnaire regarding the investigational products they have been using in this trial (see Appendix 13.1). CCI

7.3.6 Study drug acceptability questionnaire

At weeks 12 and 24/Early termination, subjects will complete an acceptability questionnaire regarding use of the study drug (see Appendix 13.2).

8 CLINICAL TRIAL VISITS DESCRIPTIONS AND PROCEDURES

8.1 Description of clinical trial visits

Please refer to the Schedule of Assessments table in the Synopsis (Table 2).

CCI

A written, dated, initialed and signed ICF, Assent Form for minors, HIPAA, and Photo Consent Form or Photo Assent form, must be obtained prior to performing any clinical trial-related evaluations and/or procedures.

CCI

CCI

CCI

CCI

CCI

CCI

CCI

CCI

8.1.9 **Unscheduled visits**

An unscheduled visit may occur for safety reasons.

During these visits, the assessments will be conducted as appropriate depending on the reason for the visit.

CCI

CCI

9 STATISTICAL METHODS PLANNED

9.1 Statistical analysis plan

A statistical analysis plan (SAP) will be developed and issued as a separate document. The SAP will contain a more detailed and technical description of specific data conventions, calculations and of statistical procedures for executing the analysis strategies that are specified in the sections of the clinical trial outline below. The SAP will be finalized prior to the database lock. CCI

CCI

[figure not shown]
Any changes to analyses made after the SAP has been finalized, along with an explanation as to when and why they occurred, will be documented in the clinical study report. Post hoc exploratory analyses will also be clearly identified in the Clinical Study Report (CSR).

9.1.1 Data transformations

Not applicable

9.1.2 Populations analyzed, evaluability and limitation / evaluation of bias

The Intention-to-Treat (ITT) population will be used for the analyses of efficacy endpoints CCI

9.1.3 Data presentation and graphics

For statistical analyses purpose, baseline is defined as the last measurement prior to the first application of the study drug and all analyses will be summarized by visits.

For the summary statistics, the categorical data will be summarized by frequency and percentage of subjects for each response category (N, %) and the continuous data will be summarized using number of subjects, mean, median, minimum, maximum, and standard deviation.

Subject disposition, demographics and baseline characteristics, previous therapies, and concomitant therapies will be summarized by descriptive statistics based on the ITT Population. Treatment exposure and compliance data will be summarized based on the Safety Population.

For statistical analysis purposes, previous therapies/procedures are defined as those ending at Baseline or before; and concomitant therapies/procedures are defined as those ongoing at the Baseline visit or starting after the Baseline visit.

Treatment-emergent Adverse Events (TEAEs) are defined as AEs with onset on or after first dose of study drug; or those AEs with onset prior to first dose of study drug but worsened during treatment.

TEAEs will be tabulated in frequency tables by System Organ Class (SOC) and Preferred Term (PT) based on the Medical Dictionary for Regulatory Activities (MedDRA). Additional summary tables will be provided for SAEs, AEs considered related to the study drug, severe AEs, AESIs, and AEs leading to discontinuation. For a given AE, a subject will be counted once even if he/she has experienced multiple episodes of that particular AE.

In addition, non TEAEs will be summarized or listed separately.

For local tolerability (erythema, scaling, dryness, stinging/burning), data will be summarized for worst score over treatment period, the final score during treatment, as well as scores for each visit.

The quality of life indices, EQ-5D-5L, COMPAQ (including the anchor question), C-DLQI, and DLQI will be summarized descriptively.

Subgroup analyses will be explored by analysis center, age (<18 years, ≥18 years), gender and race if appropriate for efficacy endpoint, and safety endpoints (TEAEs and Local tolerability).

Further details will be provided in the SAP.

9.1.3.1 *Imputation of missing data*

The last observation carried forward (LOCF) will be used to impute efficacy endpoints, where applicable. Non-responder analysis will also be carried out for Binary endpoints.

Further details will be provided in the SAP.

9.1.3.2 *Statistical hypothesis testing and multiplicity adjustment*

Analysis of Efficacy Endpoint

All efficacy and patient reported endpoints will be summarized with point estimate and 95% confidence intervals.

Further details will be provided in SAP.

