Analysed variables	
Subject-reported outcomes
 
 DLQI/cDLQI and CompAQ at Baseline and Week 12, 24/Early termination Subject satisfaction questionnaires at Week 12, 24/Early termination EQ-5D-5L at baseline and Week 12, 24/Early termination 
Efficacy variable
 
 CCI [REDACTED] Percent change in the facial IL NI CCI [REDACTED] lesion count from Baseline to Weeks 12 and 24 CCI [REDACTED] Percent change in the trunk IL, NI CCI [REDACTED] lesion count from Baseline to Weeks 12 and 24 Success rate of IGA as the percentage of subjects who achieved an IGA with a score of 1 (almost clear) or 0 (Clear) AND an at least a 2-grade improvement from Baseline at each study visit. Success rate of PGA as the percentage of subjects who achieved a PGA with a score of 1 (almost clear) or 0 (Clear) AND an at least a 2-grade improvement from Baseline at each study visit. 
CCI [REDACTED]
 
CCI [REDACTED]
 
Safety variables
 
 Local tolerability parameters will be assessed at Baseline and each post baseline visits, on all treated areas. CCI [REDACTED] Local tolerance: Raw value at each visit and worst-score across visit, % of Subjects across scores at each post-baseline visit Incidence of adverse events (AESI, SAEs, Death, leading to discontinuation or early termination) 
Other
 
CCI [REDACTED]

Principal statistical method:	
The Intent-to-Treat (ITT) population consists of all enrolled subjects. The Safety population (SAF) consists of the ITT population, who applied at least one dose of treatment.
 
The main objective of this study is to evaluate the subject reported outcomes with trifarotene with 12 and up to 24 weeks of treatment.
 
All variables will be descriptively summarized. All safety endpoints will be summarized based on SAF population and Quality of life and Efficacy endpoints will be summarized

SYNOPSIS	
Clinical Trial Title: A Multi-Center Study to Evaluate Subject Reported Outcomes with use of Trifarotene 50 µg/g Cream in the Treatment of Moderate Facial and Truncal Acne Vulgaris	

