6.4 Dose modification

Subjects are encouraged to use from the Baseline visit and throughout the study the provided moisturizer, CCI

[REDACTED]

Signs and symptoms of local cutaneous irritation assessed with a local tolerability scale will be considered as Adverse Events CCI

[REDACTED]

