7.2.1 Local tolerability assessment (of face and of trunk)

Erythema, scaling, dryness will be evaluated by the investigator separately on the face and trunk,

CCI

These tolerability signs and symptoms will be assessed for the face and the trunk separately and will be graded at baseline and at each follow up visit based on the below scale:

Erythema – abnormal redness of the skin		
None	0	No erythema
Mild	1	Slight pinkness present
Moderate	2	Definite redness, easily recognized
Severe	3	Intense redness
Scaling – abnormal shedding of the stratum corneum		
None	0	No scaling

Mild	1	Barely perceptible shedding, noticeable only on light scratching or rubbing
Moderate	2	Obvious but not profuse shedding
Severe	3	Heavy scale production
Dryness – brittle and/or tight sensation		
None	0	No dryness
Mild	1	Slight but definite roughness
Moderate	2	Moderate roughness
Severe	3	Marked roughness
Stinging/Burning – pricking pain sensation immediately after dosing		
None	0	No stinging/burning
Mild	1	Slight warm, tingling/stinging sensation; not really bothersome
Moderate	2	Definite warm, tingling/stinging sensation that is somewhat bothersome
Severe	3	Hot, tingling/stinging sensation that has caused definite discomfort

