7.2.2.1 Definitions

7.2.2.1.1 Adverse events

According to ICH E2A, an AE is any untoward medical occurrence in a subject or clinical investigation subject administered a pharmaceutical product and which does not necessarily have a causal relationship with this treatment. An AE can therefore be any unfavorable and unintended sign (including an abnormal laboratory value), symptom, or disease temporally associated with the use of a medicinal (investigational) product, whether or not related to the medicinal (investigational) product.

Thus any new sign, symptom or disease, or any clinically significant worsening of an existing sign, symptom or disease compared to the condition at the first visit (including disease treated), should be considered as an AE. Lack of efficacy is not considered as an AE.

Each new episode of a chronic disease (e.g., hay fever, allergy, etc.) should be reported as a new AE.

Notes:

- Any new sign or symptom reported by the subject that appears after accidental or intentional overdose or misuse should also be reported as an AE.
- There should be an attempt to report a diagnosis rather than the signs, symptoms or abnormal laboratory values associated with the report of an AE. However, a diagnosis should be reported only if, in the Investigator's judgment, it is relatively certain. Otherwise, symptoms, signs, or laboratory values should be used to describe the AE.
- Pregnancy is not to be considered as an AE; however, is an important medical event that must be monitored as described in Section [7.2.2.2.5](#).

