8.2. Subject Reported Efficacy Assessments

8.2.1. Dermatology Life Quality Index (DLQI):

DLQI is a validated 10-item questionnaire for subjects aged > 16 years, covering domains including symptoms/feelings, daily activities, leisure, work/school, personal relationships and treatment. DLQI data will be recorded in the CRF.

The total DLQI score is calculated by summing the scores of each question, resulting in a maximum of 30 and a minimum of 0. A lower score on the DLQI indicates increased QOL; therefore, negative changes

CCI

CCI

from Baseline indicate improvement. The DLQI total scores (which measure the impact of skin disease on the quality of life of an affected person) can be interpreted as: no effect (0-1), small effect (2-5), moderate effect (6-10), very large effect (11-20), or extremely large effect (21-30).

DLQI will be summarized by visit (Baseline, Week 12 and Week 24/ET) and as continuous variables. Absolute change from baseline will also be included in the descriptive analysis. All DLQI data will be listed.

8.2.2. Children's Dermatology Life Quality Index (cDLQI):

cDLQI is a comparable validated 10-item questionnaire designed for pediatric subjects aged 16 years or less. cDLQI will be reported at Baseline, Week 12 and Week 24/ET.

The total cDLQI score is calculated by summing the scores of each question, resulting in a maximum of 30 and a minimum of 0. A lower score on the cDLQI indicates increased QOL; therefore, negative changes from Baseline indicate improvement. The cDLQI total scores (which measure the impact of skin disease on the quality of life of an affected person) can be interpreted as: no effect (0-1), small effect (2-6), moderate effect (7-12), very large effect (13-18), or extremely large effect (19-30).

cDLQI will be summarized by visit (Baseline, Week 12 and Week 24/ET) as continuous variables. Absolute change from baseline will also be included in the descriptive analysis. All cDLQI data will be listed.

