11.5. Other Safety

11.5.1. Local Tolerability

Local tolerability (irritation) parameters (erythema, scaling, dryness and stinging/burning) will be evaluated at each visit on a 4-point scale between 0 (none), 1 (mild), 2 (moderate) and 3 (severe). The assessments will be conducted separately for the face and trunk.

CCI

Summary tables will be presented separately for face CCI and trunk CCI, using both frequency tables and descriptive statistics.

CCI

Mean values of erythema, scaling, dryness and stinging/burning on face and trunk will be presented using line plots over time.

CCI

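### The readable tolerability summaries are raw scores, and none is compared with the subject's own baseline, although every sign is graded at baseline and there is no control arm

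*Protocol*

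**What the plan says.** Protocol 7.2.1 has the four signs assessed separately for face and trunk, and they "will be graded at baseline and at each follow up visit based on the below scale". A baseline value is therefore planned for each sign in each region.

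The planned summaries appear in two places in the protocol. Section 9.1.3 states that "data will be summarized for worst score over treatment period, the final score during treatment, as well as scores for each visit". The Synopsis, under the safety variables, lists "Local tolerance: Raw value at each visit and worst-score across visit, % of Subjects across scores at each post-baseline visit".

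The readable part of SAP 11.5.1 adds that the tables are presented "using both frequency tables and descriptive statistics", and that "Mean values of erythema, scaling, dryness and stinging/burning on face and trunk will be presented using line plots over time". Other parts of that section are redacted, as is the SAP's index of tables.

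Baseline comparisons are written out elsewhere. The Synopsis plans percent change from baseline for lesion counts and compares the quality-of-life scores with baseline. In SAP 8.2 the text for DLQI, cDLQI, CompAQ and EQ-5D-5L says "Absolute change from baseline will also be included in the descriptive analysis".

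SAP 3.4 describes the trial as open label with a single arm.

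**The concern.** Without a control arm, the subject's own baseline is the only internal reference for irritation on treatment. A worst score of 1 or 2 may be a sign that appeared after the first application, or one that was there before it. A raw score does not distinguish them. The mean plot has a related weakness: if redness fades in some subjects while others become irritated, the two movements cancel and the curve can fall.

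Tolerability is one of the two safety endpoints in SAP 4.3. Protocol 1.1 names skin irritation as a cause of poor compliance and lost efficacy. It also says that managing irritation was not specifically evaluated during clinical development. SAP section 2 foresees use of the outputs in regulatory submissions, publications and promotional material, so these percentages are likely to be read on their own.

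**Working it through.** The documents state no tolerability rate, at baseline or later, so there is no planned figure to reproduce. The check is what a raw percentage would show under stated assumptions.

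**Inputs**
- n = 50 enrolled (Protocol Synopsis and 9.2).
- b = share of subjects with score at least 1 at baseline. Assumed; not in the documents.
- w = share whose score rises above their own baseline, taken as the same whatever the baseline score. Assumed.
- A baseline sign is still present at one or more post-baseline visits. Assumed. The first such visit is Week 1 (Protocol 3.2), so persistence to Week 1 is enough.

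**Worst score of at least 1**

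Raw share = b + (1 - b)w. Share truly worsening = w. Excess = b + (1 - b)w - w = b(1 - w).

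| b | w | Raw share | Truly worsening | Excess (points) |
|---|---|---|---|---|
| 10% | 20% | 28% | 20% | 8 |
| 30% | 20% | 44% | 20% | 24 |
| 50% | 20% | 60% | 20% | 40 |
| 20% | 30% | 44% | 30% | 14 |
| 40% | 30% | 58% | 30% | 28 |
| 60% | 30% | 72% | 30% | 42 |

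Over b = 10% to 50% and w = 0% to 40%, the excess runs from 0.10 × 0.60 = 6 points to 0.50 × 1.00 = 50 points. At w = 0 the raw share equals b although nobody worsened. At b = 0 the two shares coincide.

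With n = 50, b = 30% and w = 20%, the raw figure is 22/50 = 44% (95% Clopper-Pearson interval 30% to 59%). The baseline-referenced figure is 10/50 = 20% (10% to 34%).

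**Worst score of at least 2**

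Assume baseline scores of 0, 1 and 2 in 60%, 30% and 10% of subjects, with 30% of each group rising one grade. Worst score at least 2 is 10% + 0.30 × 30% = 19%. Newly at least 2 is 0.30 × 30% = 9%.

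**Mean curve**

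If 40% fall by one grade and 30% rise by one, the mean change is 0.30 - 0.40 = -0.10. The plotted mean improves although 30% of subjects worsened.

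**The case against.** A reader might infer that tolerability is analysed only as raw scores, and that signs present before treatment are counted as irritation caused by trifarotene. The documents do not support that reading, for these reasons.

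- **Redaction.** SAP 11.5.1 and the SAP's index of tables are partly or wholly blacked out, and the Synopsis has a redaction next to its tolerability bullet. Text that cannot be read cannot be called absent.
- **The protocol is an outline.** Section 9.1.3 leaves detail to the SAP. For quality of life it promises only a descriptive summary, and the SAP then adds change from baseline. The same may have happened for tolerability in the redacted text.
- **No attribution.** No readable sentence labels a raw score as drug-caused. By-visit tables may also include baseline and so show the group's starting distribution.
- **Adverse events are referenced to baseline.** Protocol 7.2.2.1.1 includes "any clinically significant worsening of an existing sign, symptom or disease compared to the condition at the first visit", and 6.4 says "Signs and symptoms of local cutaneous irritation assessed with a local tolerability scale will be considered as Adverse Events", followed by redacted text.
- **Baseline signs may be rare.** The grade 3 wording of the IGA and PGA describes lesions and does not mention redness, scaling or dryness. Stinging/burning is defined as a sensation felt just after application, so the point concerns mainly the other three signs.

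These arguments remove the word only and any claim of attribution, and they leave the size open. They do not remove the point. For tolerability the protocol gives a specific list, and the Synopsis calls the values raw while naming baseline for other outcomes. A by-visit table that includes baseline still cannot show which subjects worsened. The adverse event route depends on a judgement of clinical significance, so it does not summarise the graded scale. Subject listings allow a comparison by eye, but they are not a planned summary.

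**Conclusion.** The point holds in a limited form. The protocol's stated tolerability summaries are raw worst, final and per-visit scores, and no readable text in either document compares them with the subject's own baseline. Whether the redacted part of SAP 11.5.1 does so is unknown.

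The consequence is conditional. If baseline erythema, scaling or dryness is not zero and persists into treatment, raw worst-score percentages exceed the share that worsened, by b(1 - w) under the assumptions above. Mean curves can also mask worsening in a subset. All values of b and w are assumed, so the figures show the mechanism and do not predict this trial's results. If baseline scores are near zero, the raw and baseline-referenced percentages agree.

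This is a free improvement to a descriptive safety analysis. It does not invalidate the planned tables.

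**What to change.** In Protocol 9.1.3, and in SAP 11.5.1 unless its redacted text already has this, add for each sign, separately for face and trunk:

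1. a shift table of baseline score by worst post-baseline score and by final post-baseline score;
2. n (%) of subjects whose worst post-baseline score is above their own baseline. The denominator is subjects with a baseline and at least one post-baseline score, since SAP 6.3 plans no imputation for safety.

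Report these alongside the planned raw-score tables and mean plots, which stay as they are. If the redacted SAP text already contains such a comparison, only the protocol's list needs to be brought into line.

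The cost is a few lines of text and one extra table per region. All the data are already collected, and no visit, assessment or procedure changes.

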9.2 Sample size determination

There is no formal hypothesis to be tested. An estimation approach will be performed. Point estimate and 95% confidence interval will be constructed. Approximately 50 subjects will be enrolled to evaluate the subject reported outcomes (quality of life and satisfaction survey).

10 TRAINING / MONITORING / DATA MANAGEMENT / QUALITY ASSURANCE

10.1 Personnel training

Investigators training will occur on-site during the site initiation visit. It is recommended that all investigators, other evaluators, study coordinators and other applicable personnel attend the site initiation visit. During these meetings/trainings, CCI

CCI

All sites must complete photography training and submit test photos of all required light conditions

CCI

The Investigators and study coordinators are expected to attend the Investigator receive on-site training during the site initiation visit prior to participating in the procedures and evaluations in this study. Each site will have a training record as part of the site file and Trial Master File. An Investigator Site File will be provided to each study center.

A study initiation visit will be conducted for each study center prior to enrollment of any subjects.

CRAs and other applicable personnel will be trained prior to study initiation to familiarize CRAs with the disease, the Standard Operating Procedures (SOP), the protocol and other study specific items. Team organization, communication and operational issues will also be discussed.

